5 AMENDMENTS

Modification of the protocol is prohibited without prior written agreement in the form of a protocol amendment. All amendments will be created by the Sponsor and must be approved by the institutional review board/ independent ethics committee (IRB/IEC) prior to implementation except when required to mitigate immediate safety risks or when the changes involve only logistical or administrative revisions.

Topic	Percentage
Healthcare	95%
Technology	92%
Finance	88%
Politics	85%
Entertainment	78%
Science	75%
Food	72%
Sports	68%
Business	65%
Art	62%
History	58%
Music	55%
Geography	52%
Mathematics	48%
Chemistry	45%
Physics	42%
Biology	38%
Physics	35%
Chemistry	32%
Biology	28%
Mathematics	25%
Geography	22%
History	18%
Art	15%
Music	12%
Business	10%
Sports	8%
Food	5%
Science	3%
Technology	2%
Healthcare	1%
Entertainment	0%

This figure consists of a collection of horizontal black bars of varying lengths, arranged in a grid-like structure. The bars are positioned in rows, with some rows having multiple bars. The lengths of the bars are not uniform, with many being relatively short and others being much longer, extending across multiple rows. The bars are set against a white background and are rendered in a solid black color.

A series of 15 horizontal black bars of varying lengths, representing data points. The bars are arranged vertically, with the longest bar at the top and the shortest at the bottom. The bars are set against a white background.

This figure is a horizontal bar chart consisting of 15 groups of bars. Each group contains 3 bars of increasing length from left to right. The bars are black on a white background. The first group has the longest bars, and the length of the bars decreases progressively in each subsequent group.

The figure consists of four vertically stacked bar charts, each with a y-axis containing 10 categories and an x-axis ranging from 0 to 100. The bars are black with thin white outlines. In all four charts, categories 1, 2, 4, 5, 6, 7, 8, 9, and 10 are at 0. Categories 3 and 11 are at 100.

- Chart 1:** Categories 1, 2, 4, 5, 6, 7, 8, 9, and 10 are at 0. Categories 3 and 11 are at 100.
- Chart 2:** Categories 1, 2, 3, 4, 5, 6, 7, 8, 9, and 10 are at 0. Categories 11 and 12 are at 100.
- Chart 3:** Categories 1, 2, 3, 4, 5, 6, 7, 8, 9, and 10 are at 0. Categories 11 and 12 are at 100.
- Chart 4:** Categories 1, 2, 3, 4, 5, 6, 7, 8, 9, and 10 are at 0. Categories 11 and 12 are at 100.

The figure consists of a grid of horizontal black bars. The bars are of varying lengths, creating a visual representation of data. The grid is composed of several rows and columns of bars. Some bars are aligned vertically, while others are not. The lengths of the bars range from very short to very long, with some being nearly full-width and others being much shorter. The overall pattern is a dense collection of horizontal lines of different lengths.

The figure consists of 10 horizontal panels, each containing a bar chart. Each panel has a vertical dashed line on the left. The bars in each panel are black and vary in length, representing data points for different categories. The panels are arranged vertically, with the first panel at the top and the last panel at the bottom.

The figure consists of 15 horizontal bars, each composed of a thick black bar and a thin white bar. The thick black bars are of varying lengths, ranging from approximately 1/3 to 1/2 of the total bar height. The thin white bars are consistently short, located at the end of each thick black bar. The bars are arranged vertically, with the first bar at the top and the last bar at the bottom. The thin white bars are positioned at the end of each thick black bar.

1. **What is the primary purpose of the study?** (Please select one)

For more information, contact the Office of the Vice President for Research and the Office of the Vice President for Student Affairs.

1

A horizontal bar consisting of a thick black rectangle with a thin white square centered within it. A vertical black bar extends downwards from the center of the white square.

11. **What is the primary purpose of the *Journal of Clinical Endocrinology and Metabolism*?**

111

1. **What is the primary purpose of the study?**

© 2013 by the author; licensee MDPI, Basel, Switzerland. This article is an open access article distributed under the terms and conditions of the Creative Commons Attribution license (<http://creativecommons.org/licenses/by/3.0/>).

For more information, contact the Office of the Vice President for Research and Economic Development at [contact] or [contact].

—

For more information, contact the Office of the Vice President for Research and the Office of the Vice President for Student Affairs.

A thick black horizontal bar with a vertical black bar on the far left.

For more information, contact the Office of the Vice President for Research and the Office of the Vice President for Student Affairs.

For more information, contact the Office of the Vice President for Research and the Office of the Vice President for Student Affairs.

For more information, contact the Office of the Vice President for Research and the Office of the Vice President for Student Affairs.

For more information, contact the Office of the Vice President for Research and the Office of the Vice President for Student Affairs.

For more information, contact the Office of the Vice President for Research and the Office of the Vice President for Student Affairs.

1. **What is the primary purpose of the study?**

Print Date:

[REDACTED]

[REDACTED]

[REDACTED]

[REDACTED]

A thick black horizontal bar with a smaller black rectangle at the top left.

Term	Percentage
GMOs	~85%
Organic	~95%
Natural	~95%
Artificial	~85%
Organic	~95%
Natural	~95%
Artificial	~85%
Organic	~95%
Natural	~95%
Artificial	~85%
Organic	~95%
Natural	~95%
Artificial	~85%

113
114

THE JOURNAL OF CLIMATE

11. **What is the primary purpose of the *Journal of Clinical Endocrinology and Metabolism*?**

For more information, contact the Office of the Vice President for Research and the Office of the Vice President for Student Affairs.

Black box

1

[REDACTED]

[REDACTED]

[REDACTED]

6 SCHEDULE OF VISITS

Visit	Both Eyes	1 st Operative Eye		2 nd Operative Eye		Both Eyes												
	Visit 0	Day -28-0 Preoperative	Visit 00 ¹	Day 0 Operative	Visit 1	Day 1-2 Post Visit 00	Visit 2	Day 7-14 Post Visit 00	Visit 00A ²	Day 7-14 Days Post Visit 00	Visit 1A	Day 1-2 Post Visit 00A	Visit 2A	Day 7-14 Days Post Visit 00A	Visit 3A	Day 30-60 Days Post Visit 00A	Visit 4A ³	120-180 Days Post Visit 00A
General Assessments and Procedures																		
Informed Consent	X																	
Demographics	X																	
Medical History	X																	
Concomitant Medications	X	X	X	X	X	X	X	X	X	X	X	X	X	X	X	X	X	
Urine Pregnancy Test ⁴	X																	
Inclusion/Exclusion	X	X				X												
Ophthalmic Assessments																		
QUVID questionnaire (for visual disturbance)	X														X	X	X	
IOLSAT questionnaire (for spectacle need)	X													X	X	X	X	
Anterior Chamber Depth	X																	
Axial Length	X																	
Keratometry	X																	
Predicted Target Residual Refractive Error ⁵	X																	
Manifest Refraction (4 m)	X				X						X	X	X	X	X	X	X	
Distance VA at 4 m																		
• Photopic Uncorrected	X		X	X			X	X			X	X	X	X	X ⁶	X		
• Photopic Corrected	X			X							X	X	X	X	X ⁶	X		
	■	■■■■■													■			
	■	■■■■■													X			
Defocus Curve (4 m)															X ⁶			
		X													X			
Intermediate VA at 66 cm																		
• Photopic Uncorrected														X	X ⁶			
• Photopic Distance Corrected													X	X ⁶				
	■	■■■■■													X			

	Both Eyes	1 st Operative Eye			2 nd Operative Eye			Both Eyes		
		Visit 0 Day -28-0 Preoperative	Visit 00 ¹ Day 0 Operative	Visit 1 Day 1-2 Post Visit 00	Visit 2 Day 7-14 Post Visit 00	Visit 00A ² 7-14 Days Post Visit 00	Visit 1A Day 1-2 Post Visit 00A	Visit 2A 7-14 Days Post Visit 00A	Visit 3A 30-60 Days Post Visit 00A	Visit 4A ³ 120-180 Days Post Visit 00A
Visit										
■ [REDACTED]										X
Near VA at 40 cm										
• [REDACTED]									X	X ⁶
• Photopic Distance Corrected									X	X ⁶
■ [REDACTED]										■
■ [REDACTED]									X	
■ [REDACTED]									X	
Contrast Sensitivity										
• Mesopic without Glare									X	
• Mesopic with Glare									X	
Slit Lamp Examination	X		X	X		X	X	X	X	X
Aqueous Signs			X	X		X	X	X	X	X
IOL Observations			X	X		X	X	X	X	X
IOL Position Change			X	X		X	X	X	X	X
Subjective PCO			X	X		X	X	X	X	X
Posterior Capsulotomy				X	X		X	X	X	X
Intraocular Pressure	X		X	X		X	X	X	X	X
Dilated Fundus Exam	X							X	X	X
Fundus Visualization								X	X	X
Surgical Procedure & Assessments										
Cataract Surgery		X				X				
Lens Information		X				X				
Incision Location ⁷		X				X				
Final Incision Size ^{7,8}		X				X				
Problems during Surgery		X				X				
Other Surgical Procedures		X				X				
Adverse Events & Device Deficiencies										
Adverse Events ⁹	X	X	X	X	X	X	X	X	X	X
Secondary Surgical Interventions		X	X	X	X	X	X	X	X	X

Visit	Both Eyes	1 st Operative Eye			2 nd Operative Eye			Both Eyes		
		Visit 00 ¹ Day 0 Preoperative	Visit 1 Day 0 Operative	Visit 2 Day 1-2 Post Visit 00	Visit 00A ² 7-14 Days Post Visit 00	Visit 1A Day 1-2 Post Visit 00A	Visit 2A 7-14 Days Post Visit 00A	Visit 3A 30-60 Days Post Visit 00A	Visit 4A ³ 120-180 Days Post Visit 00A	
Device Deficiencies		X	X	X	X	X	X	X	X	X

1. Visit 00 (1st eye surgery) must occur within 28 calendar days from Pre-Operative Visit (Visit 0).
2. Visit 00A (2nd eye surgery) must occur between 7 and 14 calendar days after Visit 00.
3. If necessary, Visit 4A may be completed over 2 days within a two-week period. Both days must fall within the specified visit window.
4. In women of child bearing potential only.
5. Data is reported in EDC at the surgical visit, but may be collected at a previous visit.
6. Testing is conducted monocular (bilaterally) [REDACTED].
7. Capture in source (not captured in EDC).
8. Only measure in cases with surgical complications.
9. Collected from time of consent onward.

7 INTRODUCTION

7.1 Background

Depth of focus (DOF) is the amount of focal plane displacement behind a lens that does not degrade the image quality of a distant object. The distance between the nearest and farthest objects in a scene that appear acceptably sharp depends upon the eye's DOF. Larger DOF allows sharp images of closer objects. A young, healthy human eye provides large DOF due to the large range of accommodation of the crystalline lens; however, the amplitude of depth of focus or accommodation gradually declines with age. For most people, accommodation is completely lost in the mid-fifties. While subjects implanted with a monofocal IOL have good distance vision, quality of vision at intermediate and near is often insufficient to support activities of daily living

Premium IOL solutions, such as multifocal IOLs, provide functional intermediate vision and near vision, but can also result in complaints of visual disturbance. In view of this, there exists a medical need to provide functional vision at intermediate and near distances, while maintaining good distance vision and a visual disturbance profile similar to that of a monofocal IOL. The ACRYSOF IQ EDF IOL was developed to provide an extended depth of focus at intermediate distance (approximately 66 cm) while maintaining distance VA and a safety profile similar to that of the ACRYSOF IQ Monofocal IOL.

A summary of known and potential risks and benefits to humans, as identified in the literature or through preclinical testing and/or prior clinical evaluations, for each investigational product can be found in the respective Directions for Use (DFU) - ACRYSOF IQ model

SN60WF, ACRYSOF IQ EDF model DFT015. Additional relevant information on the test article can be found in the Investigator's Brochure.

7.2 Purpose of the Study

The ACRYSOF IQ EDF IOL was developed to provide an extended DOF for provision of functional intermediate and near vision while maintaining both a distance VA and a safety profile similar to that of the ACRYSOF IQ Monofocal IOL. The purpose of the study is to demonstrate the safety and performance of ACRYSOF IQ EDF IOL at Month 6/Visit 4A.

7.3 Risks and Benefits

The risk of unanticipated adverse device effects with use of ACRYSOF IQ EDF IOL is considered to be low and the benefits of receiving the IOL should outweigh the risks for subjects that qualify for implantation in this study.

7.3.1 Known and Potential Risks

Refer to the IB and DFU for comprehensive risk information on ACRYSOF IQ EDF IOL model DFT015. A summary of this information is found below.

Surgical Complications:

Complications may occur on the surgery day or throughout the postoperative period. As with any type of intraocular surgery, there is a possibility of complications due to anesthesia, drug reactions, and surgical problems. The surgical procedure can exacerbate a pre-existing ocular condition. Possible problems during surgery include corneal endothelial touch, detached Descemet's membrane, iris damage, iris prolapse, iris trauma, iris incarceration, zonular rupture, vitreous loss, capsulorhexis tear, capsular rupture, uncontrollable intraocular pressure (IOP), hyphema, and retinal damage. An IOP increase may occur from the surgical procedure, residual viscoelastic in the eye, or a steroid response to postoperative medications.

Additionally, potential postoperative adverse events include but are not limited to corneal stromal edema, cystoid macular edema, endophthalmitis, hypopyon, iritis, lens dislocation, membrane formation on the IOL, pupillary block, retinal detachment, cyclitic membrane, transient or persistent glaucoma, retinal tear, vitritis, iris touch, pupil ovalization, posterior synechiae, ocular inflammation, ocular discomfort or pain, inflammation, decreased vision, decreased contrast sensitivity, decreased color perception, visual disturbances, and corneal endothelial cell loss.

ACRYSOF IQ EDF IOL Model DFT015:

An IOL replacement or explantation may be appropriate in some cases of significant residual refractive error, ocular infection, subject dissatisfaction, or visual disturbances (eg, glare, halos, starbursts, hazy vision, blurred vision, double vision, visual distortions, and color distortions). In most/majority of cases, spectacles or contact lenses may be prescribed to resolve residual refractive error. Other secondary surgical interventions include, but are not limited to: IOL repositioning, refractive laser treatment, paracentesis, vitreous aspirations, and iridectomy or laser iridotomy for pupillary block, wound leak repair, and retinal detachment repair.

There may also be unknown risks with the use of the ACRYSOF IQ EDF IOL. Any foreseen risk to subjects in this clinical study will be minimized by compliance with the eligibility criteria, study procedures, and clinical monitoring.

7.3.2 Potential Benefits

[REDACTED]
[REDACTED]
[REDACTED] The ACRYSOF IQ EDF IOL may provide benefits to the subject by:

- Extending the range of functional vision to intermediate distances
- Maintaining the distance VA and safety profile similar to ACRYSOF IQ Monofocal IOL
- Providing improved near vision in comparison to a monofocal IOL
- Eliminating the visual disturbances commonly associated with diffractive IOLs

8 CLINICAL TRIAL OBJECTIVES

8.1 Primary Effectiveness Objective(s)

Below are listed the study's co-primary objectives. Each objective is assessed at Visit 4A (120-180d postoperative).

1. To demonstrate ACRYSOF IQ EDF IOL is superior to ACRYSOF IQ Monofocal IOL in mean monocular photopic DCIVA
2. To demonstrate that ACRYSOF IQ EDF IOL is non-inferior to ACRYSOF IQ Monofocal IOL in mean monocular photopic BCDVA
3. To demonstrate that the monocular mean defocus curve for ACRYSOF IQ EDF IOL has a range of defocus at least 0.5 D greater negative range than ACRYSOF IQ Monofocal IOL at 0.2 logMAR
4. To demonstrate that ACRYSOF IQ EDF IOL has at least 50% of eyes achieving DCIVA of 0.2 logMAR or better

A successful outcome on the co-primary effectiveness endpoints is indicated by successful outcomes on all 4 of these endpoints.

8.1.1 Primary Effectiveness Endpoint(s)

Below are listed the study's primary effectiveness endpoints.

1. Monocular photopic DCIVA (logMAR) 66 cm from spectacle plane
2. Monocular photopic BCDVA (logMAR)
3. Monocular depth of focus (measured in the negative direction from 0) at 0.2 logMAR
4. Percentage of eyes achieving monocular photopic DCIVA of 0.2 logMAR or better

8.2 Secondary Effectiveness Objective(s)

Below are listed the study's co-secondary objectives. Each objective is assessed at Visit 4A (120-180d postoperative).

1. To demonstrate that ACRYSOF IQ Extended Depth of Focus IOL is superior to ACRYSOF IQ Monofocal IOL in mean monocular photopic DCNVA

In addition, the following performance targets will also be assessed to demonstrate clinical significance:

- At least 50% of eyes with ACRYSOF IQ EDF IOL achieve a monocular DCNVA of 0.3 logMAR or better
- Percentage of eyes achieving monocular DCNVA of 0.3 logMAR or better in ACRYSOF IQ EDF IOL group is at least 25 percentage points higher than in ACRYSOF IQ Monofocal IOL group

- 2 To demonstrate that ACRYSOF IQ Extended Depth of Focus IOL is superior to ACRYSOF IQ Monofocal IOL with respect to proportion of subjects who respond “Never” to Q1 of the IOLSAT questionnaire (Overall, in the past 7 days, how often did you need to wear eyeglasses to see?)
- 3 To describe mean monocular photopic UCIVA outcomes
- 4 To describe mean monocular photopic UCDVA outcomes

8.2.1 Secondary Effectiveness Endpoint(s)

Below are listed the study’s secondary effectiveness endpoints.

- 1 Monocular photopic DCNVA (logMAR) 40 cm from spectacle plane
- 2 Proportion of subjects who respond “Never” to Q1 of the IOLSAT questionnaire: “Overall, in the past 7 days, how often did you need to wear eyeglasses to see?”
- 3 Monocular photopic UCIVA (logMAR) 66 cm from spectacle plane
- 4 Monocular photopic UCDVA (logMAR)

- [REDACTED]

8.3 Co-Primary Safety Objective

Below are listed the study's co-primary safety objectives. Each objective is assessed at Visit 4A (120-180d postoperative).

1. The study's primary safety objective is to demonstrate that ACRYSOF IQ EDF IOL adverse event rates are not worse than the historical control SPE rates, as defined in IS EN ISO 11979-7:2014
2. To describe monocular mesopic contrast sensitivity test (with and without glare) outcomes

8.3.1 Primary Safety Endpoint

The study's primary safety endpoints are

- Rate of ocular adverse events
- Mesopic contrast sensitivity (log units)

8.4 Secondary Safety Objective(s)

To estimate rates of severe and most bothersome (separately) visual disturbances as reported by subjects using a questionnaire at Visit 4A (120-180d postoperative)

8.4.1 Secondary Safety Endpoint(s)

The study's secondary safety endpoint is QUVID-reported visual disturbances rate.

8.4.2 Supportive Safety Endpoint(s)

Supportive safety endpoints include those bulleted below.

- IOP
- Slit lamp findings including IOL observations

- IOL tilt/decentration
- Subjective PCO assessment
- Posterior capsulotomy
- Dilated fundus exam findings including fundus visualization
- Intraoperative surgical problems
- Other procedures at surgery (combined and/or additional)
- Adverse events (including SSIs)
- Device deficiencies

9 INVESTIGATIONAL PLAN

9.1 Study Design

This is a prospective, multi-center, randomized, parallel-group, controlled, assessor- and subject-masked study. Both eyes of a subject must require cataract surgery to qualify for enrollment into this study. To reduce bias, subjects will be randomly assigned in a 1:1 ratio to receive either ACRYSOF IQ EDF IOL model DFT015 (test article) or ACRYSOF IQ Monofocal IOL model SN60WF (control article) in both eyes. To further reduce bias, all subjects and site assessors will be masked to subject treatment assignment until the end of the study.

[figure not shown]
The first operative eye is defined as the eye with the worse BCDVA. If the BCDVA is the same in both eyes, identify the right eye (OD) as the first operative eye. The second eye implant must occur within 14 days of the first eye implant.

A total of 9 scheduled visits are planned and subject participation is expected to last 7-8 months. The visits include a Screening visit (Visit 0), 2 Operative Visits (Visit 00 and Visit 00A), and 6 postoperative visits at the following intervals: Day 1-2 (Visit 1/1A), Day 7-14 (Visit2/2A), Day 30-60 (Visit 3A), and Day 120-180 (Visit 4A) (See Figure 9-1 Study Design). Primary endpoint data will be collected at the Month 6/ Visit 4A (120-180 day post 2nd eye implantation).

Note: Visit 4A may be completed over 2 days within a 2-week period. Both days must fall within the specified visit window.

Figure 9-1

Study Design Diagram

9.2 Rationale for Study Design

The study is designed to assess performance and safety parameters of interest in compliance with guidance from the draft ANSI Z80.35 Extended Depth of Focus Intraocular Lenses (11 July 2016) and the American Academy of Ophthalmology Task Force Consensus Statement for Extended Depth of Focus Intraocular Lenses (MacRae 2017). Compliance includes subject number requirement (100 per lens model), follow-up period (6 months postoperative), control article (see Section 9.3 below), randomization, masking, and assessments.

9.3 Rationale for Choice of Control Article

ACRYSOF IQ EDF IOL is a modification of the United States (US) Food and Drug Administration (FDA) approved, commercially available control article (ACRYSOF IQ Monofocal IOL). The control article has the same physical properties and is composed of the same material as the test article. Based on optical bench testing and simulation of the test article, the contrast sensitivity under mesopic conditions is expected to be comparable to the

control article. Further, the ACRYSOF IQ Monofocal IOL is well established in the literature and is considered the industry standard of care. For these reasons, the ACRYSOF IQ Monofocal IOL is scientifically the most appropriate control article for this study, and functions to reduce bias.

9.4 Data Monitoring Committee

Not applicable.

10 SUBJECT POPULATION

The study population consists of male and female subjects 22 years of age and older, with a diagnosis of cataract in both eyes, requiring surgery with implantation of a monofocal IOL in the capsular bag. It is aimed to randomize approximately 220 subjects at approximately 12 US investigative sites. Each site will aim to randomize approximately 20 subjects, and no site will randomize more than 55 subjects (25% of total). Site specific targets may be adjusted based on individual site capabilities. Enrollment projections are as follows:

- 240 subjects to be enrolled/sign consent (approximately 10% screen failure rate is expected)
- 220 subjects to be randomized (approximately 10% discontinuation rate is expected)
- 200 subjects to successfully complete the final study visit (Visit 4A)
 - 100 subjects in the ACRYSOF IQ EDF IOL arm
 - 100 subjects in the ACRYSOF IQ Monofocal IOL arm

Sites must check all entry criteria at Screening/Visit 0 and at both surgical visits (Visit 00, Visit 00A). If a subject is excluded post randomization and prior to first eye surgery (IOL does not come in contact with the eye), the subject should be discontinued from participation in the study. Refer to Section 12.6 Discontinued Subjects for further details.

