10.3 Reasons for Non-Implantation

Below are listed reasons to not implant the study lens, where study lens refers to both the test lens and the control lens.

1. Surgical complications including but not limited to loss of zonular integrity/zonular weakness, zonular rupture, anterior capsular rupture interfering with the stability of the IOL, posterior capsule rupture, any evidence of fluid misdirection during the cataract procedure with progressive shallowing of the anterior chamber, uncontrollable IOP
2. Mechanical or surgical manipulation of the pupil
3. Excessive iris mobility

4. Inability to place the IOL in the capsular bag due to surgical complications

If the study implantation is aborted due to a reason for non-implantation, follow standard of care and implant a non-study lens. In the event the first eye is not implanted and the IOL **did not** touch the eye, the subject is discontinued from the study. If the implantation is aborted and the IOL **did** touch the eye (first operative eye), then the second eye should not be implanted and the subject is encouraged to attend all follow-up study visits for safety evaluation on this eye only. In the event the second eye is not implanted, the subject continues in the study. Refer to Manual of Procedures (MOP) Section 5.4 for complete details on subject discontinuation and/or follow-up when a lens is not implanted.

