11.4 Treatment Masking

The assessor and subject will be masked in this study. Subjects will be masked to treatment assignment for the entire duration of the study. Site personnel performing the manifest refraction, all VA assessments (including defocus curve testing), and all contrast sensitivity assessments will remain masked with regard to treatment assignment until after the final database lock. Should a subject safety concern arise, refer to Section 13.10 Unmasking of the Study Treatment. **Note:** Any unmasking of assessor or subject must be reported to Alcon.

After the subject is implanted with the appropriate lens, a generic implant card is provided to the subject. The implant card will not reveal his/her treatment assignment. The treatment assignment will only be revealed to the study subject after the final database lock and when investigative sites are notified by the Study Sponsor.

Masked study personnel must avoid seeking information that may compromise masking. Unmasked study personnel must not disseminate information that is potentially unmasking to any masked personnel. A list of unmasked individuals can be found in Table 10-4 below.

Table 11-4 Unmasked Individuals

Unmasked Individual	Extent of Unmasking	Rationale
Investigator	Unmasked to IP treatment assignment	Investigator will be implanting the IOL and will have knowledge of the treatment assigned to study subjects
Site Personnel (not completing assessments noted Section 11.4)	Unmasked to IP treatment assignment	Site personnel involved with operative visits and data entry into EDC
Monitor	Unmasked to IP treatment assignment	Monitor will complete IP accountability and monitoring responsibilities

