Below is a list of study procedures to be completed at Visit 00 and Visit 00A. It is recommended that procedures are performed in the order described below unless otherwise stated. Activities involving multiple delegated staff members may be performed in parallel. All assessments must be documented in source documentation and, if applicable, eCRF.

1. In preparation for the operative visit, randomize the subject. It is recommended that subjects are contacted prior to randomization to 1) confirm willingness to continue trial participation, and 2) confirm scheduled surgical date and time.
Note: Randomization must occur within 2 business days of the scheduled first eye surgery. Lens power cannot be changed after the subject is randomized.
2. Document any changes to ocular and non-ocular concomitant medications.
3. Prior to treatment, review inclusion/exclusion criteria and ensure the subject has been properly consented for participation in the study.
4. Prepare subject for surgery in accordance to site specific operating procedures.
[Operative Eye Only, Monocular]
5. Perform surgery and implantation with the randomized IOL. *[Operative Eye Only, Monocular]* Implantation may be attempted twice. After 2 aborted implants, the subject must be implanted with a non-study IOL (IOL not provided as part of study consignment).
6. If a surgical complication occurs, measure and record incision size at the completion of IOL implantation. *[Operative Eye Only, Monocular]*
7. Record incision location. *[Operative Eye Only, Monocular]*

8. Record any intraoperative surgical problems, complications or other procedures that occur during surgery. Other procedures include those performed outside of routine cataract surgery whether combined and/or additional. *[Operative Eye Only, Monocular]*
Note: Other planned procedures at the time of surgery are exclusionary.
9. Record the lens information that is located on the IOL sticker. Both successful and aborted (if applicable) test and control article information should be recorded. *[Operative Eye Only, Monocular]*
10. Evaluate for and record any AEs including SSIs. Refer to Section 13 for further detail.
11. Evaluate for and record any DDs. Refer to Section 13 for further detail.

12.2.4 1-Day Postoperative Visit (Visit 1/1A)

Visit 1: 1-2 Day Post First Eye Implantation, Monocular First Eye

Visit 1A: 1-2 Days Post Second Eye Implantation, Monocular Second Eye

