15.2 Analysis Data Sets

The primary analysis set for effectiveness analyses will be the all-implanted analysis set (AAS). AAS includes all randomized eyes with successful IOL implantation.

Additional supportive analyses will be conducted using the best-case analysis set (BAS). BAS includes all eyes successfully implanted that had

- at least 1 postoperative visit
- no preoperative ocular pathology
- no macular degeneration detected at any time
- no previous surgery for the correction of refractive errors
- no major protocol violation

The Safety Analysis Set will include all eyes with attempted IOL implantation (successful or aborted after contact with the eye).

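### Entry criteria are re-checked after randomisation by an unmasked investigator, and any first eye not implanted leaves the primary analysis set, so exclusions can depend on the assigned lens

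*Protocol*

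**What the plan says.** **Order of steps.** Section 11.2 lets the investigator or a delegate start randomisation in the EDC system once eligibility is confirmed and powers for both lens models are chosen. Section 12.2.3 makes randomisation step 1 of the operative visit: "Randomization must occur within 2 business days of the scheduled first eye surgery". Step 3 follows: "Prior to treatment, review inclusion/exclusion criteria and ensure the subject has been properly consented for participation in the study". Section 10 likewise requires all entry criteria to be checked at Visit 0 and again at both surgical visits.

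**Who knows the assignment.** Table 11-4 in Section 11.4 gives the reason for unmasking: "Investigator will be implanting the IOL and will have knowledge of the treatment assigned to study subjects". The protocol does not say when the surgeon learns the assignment.

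**What is re-checked.** Inclusion criterion 8 is the investigator's opinion that each eye can reach a corrected distance acuity of 0.2 logMAR after surgery. Exclusions 1, 3, 4 and 10 also turn on investigator judgement. Section 10.3 adds an open-ended list of surgical complications and items without a threshold, such as "Excessive iris mobility".

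**What follows from exclusion.** Before first-eye surgery: "If a subject is excluded post randomization and prior to first eye surgery" without lens contact, "the subject should be discontinued from participation in the study". Section 12.6.2 treats a first eye that is not implanted and not touched by the lens as a discontinuation and does not replace the subject. A first eye aborted after lens contact stays in safety follow-up (Sections 10.3 and 12.6.3). If only the second eye is not implanted, the subject continues.

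**Analysis sets (Section 15.2).** "AAS includes all randomized eyes with successful IOL implantation". The best-case set also requires successful implantation, and the safety set requires an attempt with lens contact.

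**The concern.** A randomised comparison is protected only if removal of subjects after randomisation cannot depend on the arm. Here the re-check follows assignment, the person whose opinion the criteria invoke is unmasked, and some of those opinions concern the quantity that a co-primary endpoint measures. A subject judged unlikely to see well can be dropped on that judgement, and the first eye then leaves the comparison.

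Two kinds of result are exposed. BCDVA non-inferiority is the least-powered co-primary test (stated power 84%), with 0.06 logMAR between the planned difference and the margin. The performance targets are judged on point estimates (Section 15.4), so a few eyes near the threshold can decide them. The co-primary target of at least 50% of test eyes with DCIVA of 0.2 logMAR or better is the clearest case. Masked subjects and assessors protect how acuity is measured at Visit 4A, not which eyes get there.

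**Working it through.** **1. Does the opening exist?** Set side by side:

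| Step | Place | Content |
|---|---|---|
| Eligibility first confirmed | 11.2; 12.2.2, step 16 | Before randomisation |
| Randomisation | 12.2.3, step 1 | Up to 2 business days before surgery |
| Criteria re-checked | 10; 12.2.3, step 3 | After randomisation, investigator unmasked |
| Non-implantation list applied | 10.3 | During surgery, by the unmasked surgeon |
| Primary set formed | 15.2 | Successfully implanted eyes only |

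A subject removed before lens contact is in none of the three analysis sets. A first eye aborted after contact is in the safety set but not in the AAS.

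**2. The plan's own figure.** Inputs from the synopsis sample-size section: 100 per arm, difference 0.04, SD 0.16, margin 0.10, one-sided 5%.

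- SE = 0.16 × √(2/100) = 0.0226
- Power = Φ((0.10 − 0.04)/0.0226 − 1.645) = Φ(1.007) = 0.843, which agrees with the stated 84%.

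**3. Illustration for BCDVA. None of the removal inputs below comes from the protocol.** Assume 110 randomised per arm (220 at 1:1), SD 0.16, and a true all-randomised difference exactly at the 0.10 margin. Assume k test eyes are removed whose BCDVA would have averaged g = 0.2 to 0.3 logMAR worse than their arm's mean. No control eyes are removed and there are no other losses.

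- Shift in the retained test mean = k·g/(110 − k)
- SE = 0.16 × √(1/(110 − k) + 1/110)
- Type I error ≈ Φ(shift/SE − 1.645)

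For k = 3 and g = 0.2: shift = 0.6/107 = 0.0056, SE = 0.0217, type I error = Φ(−1.387) = 8.3%.

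| k removed | Shift in mean (logMAR) | Shift as share of 0.06 | Type I error (nominal 5%) |
|---|---|---|---|
| 1 | 0.002-0.003 | 3-5% | 5.9-6.5% |
| 3 | 0.006-0.008 | 9-14% | 8.3-10.4% |
| 5 | 0.010-0.014 | 16-24% | 11.3-16.1% |
| 10 | 0.020-0.030 | 33-50% | 23.0-38.7% |

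The last row is an extreme bound. Ten eyes is the whole planned loss per arm from all causes (20 of 220 randomised, or 10 per arm). If the same number of equally poor eyes were removed from both arms, the shifts would cancel.

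**4. Illustration for the 50% DCIVA target.** If all k removed test eyes would have failed and exactly half of the retained eyes pass, the all-randomised rate is 0.5 × (110 − k)/110. For k = 3, 5 and 10 this is 48.6%, 47.7% and 45.5%, yet the target is met in each case.

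**The case against.** The strongest reply is that eligibility is not first decided with the lens known. Section 11.2 requires it to be confirmed before randomisation, and both lens powers are fixed by then. The Visit 00 list contains no acuity, slit-lamp or fundus examination before surgery. An investigator who now doubted the expected acuity would be reversing a documented Visit 0 judgement without a new protocol measurement. This stands and narrows the opening to a late re-check. It does not close it, because the protocol requires that re-check and the discontinuation that follows from a failure.

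The 10.3 items are mostly surgical or anatomical events. Section 9.3 says the two lenses share physical properties and material, so the documents give no device reason for the list to be applied differently by arm. Nor do they show that an eye meeting a 10.3 item would have had poor acuity at Visit 4A. This also stands: differential use of 10.3 is possible but not indicated.

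A reader might infer that everyone removed leaves both the study and every analysis. That is too broad. Eyes aborted after contact stay in safety follow-up and in the safety set, and a missed second eye leaves the first eye in the primary analysis.

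Finally, discontinuation reasons are already recorded (Section 12.6.2), and Section 15.5 leaves the details of the missing-data analyses to an SAP that is not shown. A by-arm table or a wider sensitivity set may already be planned there. The order of steps, the unmasking and the AAS definition are fixed in the protocol itself.

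**Conclusion.** The point holds as a design weakness worth correcting. A mandatory re-check that includes opinions about expected acuity comes after randomisation, is open to an unmasked investigator, and feeds a primary set that drops every first eye not successfully implanted. Neither the earlier eligibility check nor assessor masking removes that route. Setting evaluability before the code is broken (Section 15.1) does not either, since site removals come first.

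The documents show an opportunity for bias. They do not show that bias occurred or is likely. They give no removal rate by arm, only about 10% loss overall, so no expected size can be stated. The illustrative type I errors of about 8-10% for three removals and 11-16% for five rest on assumed one-sided removal of eyes 0.2 to 0.3 logMAR worse than their arm. They should not be read as predictions. The 50% example is set exactly at the threshold, so it shows fragility there rather than an expected error.

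**What to change.** 1. **Sections 11.2 and 12.2.3.** Have existing unmasked site personnel make the EDC randomisation call and hold the result. Complete and record the Visit 00 entry-criteria re-check before the assignment is disclosed to the surgeon. Where feasible, also record before disclosure the decision on those 10.3 items that can be judged before lens insertion. Items that arise only at insertion, such as inability to place the lens or an aborted attempt, will remain unmasked. The clinical non-implantation rules do not change.

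2. **Sections 15.2 and 15.5.** Tabulate randomised-but-not-implanted first eyes by arm, reason and timing relative to disclosure. Add a supportive sensitivity analysis of DCIVA and BCDVA on all randomised first eyes. State its limit: outcomes for never-implanted eyes must be imputed from baseline data, and these eyes may have received a non-study lens, so the analysis asks a somewhat different question from the AAS. Prevention under item 1 is therefore worth more than this run.

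**Cost.** The lens is presented to the surgeon slightly later, and there is one extra table and one extra sensitivity run. No additional subjects or visits are needed. Table 11-4 already provides for unmasked site personnel at the operative visits.
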